### **5.3 Inclusion of Women and Minorities**

Women and minorities are welcome to participate.

### **5.4 Participation of Children**

Children younger than 18 years of age are not eligible for this trial. SCCS of the skin is exceedingly rare in this population, and it is not expected that subjects of this age group will be eligible.

### **5.5 Sources or Methods of Recruitment**

Patients will be recruited mostly from the Rutgers Cancer Institute of New Jersey/RWJUH and from physicians participating in the Cancer Institute Oncology Group (CINJOG).

### **5.6 Study Enrollment Procedures**

A copy of the institution's IRB-approved informed consent document and written justification for any changes made to the informed consent for this protocol must be on file at the Rutgers Cancer Institute of New Jersey's Office of Human Research Services (OHRs) before any participating institution may enter patients. The CINJOG institution consent form must be reviewed and approved by OHRs Regulatory Affairs and all documents must be received (i.e., IRB approved documentation, IRB approved consent form, etc.).

To register eligible patients on this study, each site will contact OHRs. Contact information will be provided at the time of site activation. The signed and dated eligibility checklist, completed signature page of the consent form and additional source documents if requested by OHRs will need to be provided. Once OHRs verifies eligibility, a unique patient study number will be issued. The patient will not be identified by name. This is the point that the patient is considered on study. Patients must not start protocol treatment prior to registration.

If a patient does not receive any protocol therapy, baseline data will be collected and submitted on the pre-study and follow-up electronic case report forms (eCRF). The reason for not starting protocol therapy will be documented in the "follow-up eCRF". Case report form completion instructions and training will be provided to each participating institution prior to study activation at the participating institution.

## 6. Study Parameters

Evaluations	Pre-cetuximab	Weekly during neoadjuvant cetuximab	Post-cetuximab (Week 9)	At surgery or prior to RT 	30 days after surgery or XRT	Follow ups every 3 months after surgery or XRT for 2 years	After locoregional or distant failure
History, physical exam and tumor site assessment	X  (within 14 days of treatment)	X 	X 		X 	X 	X 
Photo of tumor and/or rash at head, neck, upper torso put into EMR	X (within 14 days of treatment)	X 	X 				
Incisional/core biopsy of primary tumor and loco-regional lymph nodes if involved	X  (within 30 days of treatment)			X  (any time during this interval)			X (within 30 days of relapse)
Biopsy of skin	X  (within 30 days of treatment)			X  (any time during this interval)			X (within 30 days of relapse)
CBC, differential, platelets	X (within 14 days of treatment)	X			X	X	
Serum Chemistries 	X (within 14 days of treatment)	X	X	X	X	X	
Liver Enzymes 	X (within 14 days of treatment)	X			X	X	
Pregnancy Test 	X (within 14 days of treatment)						

Radiographic Assessments 	X  (within 30 days of treatment)		X 			X	X 
---------------------------------------	---	--	----------------	--	--	---	----------------

\*A +/- 2 day window is allowed for all study assessments indicated on this trial except treatment for which a +/- 1 day window is allowed.

1. To include toxicity assessment, ECOG performance status, weight
2. Includes: Electrolytes, including serum magnesium, potassium, Calcium, BUN, Creatinine, Glucose,
3. Includes: Total and Direct. Bilirubin, AST/ALT, Alkaline Phosphatase, Albumin, Total Protein.
4. Women 18-55 who have not undergone menopause must have urine pregnancy test within 14 days of enrollment.
5. Tumor assessments as indicated by investigator, i.e. PET/CT, CT neck, chest/abdomen and pelvis or MRI of neck as needed to be obtained no more than 1 month prior to cetuximab; then per standard of care, in general, every three months after conclusion of surgery or XRT.
6. Every 7 days
7. Includes evaluation by surgery and radiation oncology for optimal local therapy. Surgery will assess optimal timing of rebiopsy during their evaluation of patient once neoadjuvant therapy is complete.
8. See section 11

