### 4. Experimental Design and Methods

#### 4.1 Duration of Study

20 patients are planned to be enrolled. The patients will be under active treatment with cetuximab monotherapy for approximately 8 weeks. Afterwards, they will be assessed for disease response and determination of whether the lesion is potentially resectable will be made. We expect that patients will be accrued within 24 months and that followup time will average 18-24 months per patient.

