### 7.2.4 Repeat Bx after neoadjuvant cetuximab.

After 8 weeks of neoadjuvant cetuximab, tissue will either be harvested at surgery, or if the patient is not a surgical candidate, a biopsy specimen (preferably a core biopsy as opposed to a FNA) will be procured from the primary site or accessible lymph node. As

this tissue will be used for DNA and RNA sequencing, tissue that is fresh and sufficient in quantity is required. These specimens will be flash frozen and brought that same day to the BRS.

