## 8. Toxicity Monitoring and Adverse Event Reporting

All patients who receive one dose of protocol therapy will be evaluable for assessment of toxicity. Prior to each cycle the treating physician will fully assess the patient's condition with respect to possible treatment related toxicities. All adverse events, whether observed by the physician or reported by the patient, occurring during the active portion of therapy, or up to 30 days after the last dose of treatment will be graded by a numerical score according to the NCI's Common Terminology Criteria for Adverse Events (CTCAE), Version 4.0 (<http://ctep.cancer.gov/reporting/ctc.html>) and recorded in the patient's medical record. For the purposes of reporting laboratory abnormalities, only Grade 3-4 adverse events will be recorded on the adverse event CRF pages. Grade 1-2 laboratory abnormalities will not be recorded on the adverse event CRF pages. Information entered on the adverse event CRF pages will include:

- Specific type and duration of reaction (i.e., start and stop dates, resolution).
- Severity/grade.
- Relationship to study drug (causality, attribution).
- Management of the event, if treated with medication and other actions taken to alleviate the clinical event.
- Whether or not it was considered a SAE.

A preexisting condition is one that is present at the start of the study. A preexisting condition will be recorded as an adverse event if the frequency, intensity, or the character of the condition worsens during the study period.

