### 8.1 Adverse Event Reporting Requirements

An adverse experience is defined as any unintended or abnormal clinical observation that is not of benefit to the patient. Either the condition was not present prior to exposure to the study therapy, or it has worsened in intensity or frequency following exposure to the study therapy.

All “unexpected” (defined below) and/or “serious” (defined below) adverse events occurring during the active portion of therapy, or up to 30 days after the last dose of treatment, will be reported to the OHRS at [contact] or [contact]. Events will be promptly reported, in writing, to the local IRB in accordance with IRB policy. If a death occurs the IRB will be notified within 24-hours of initial receipt of information. All other SAEs must be reported to the IRB within three to ten days of initial receipt of information. Written follow-up reports are required when additional information is needed to fully characterize the event. Copies of each report sent to the IRB will be kept in the study regulatory file.

In addition to reporting to the local IRB, reporting to external bodies such as industry and/or the FDA may be necessary. The Oncology group affiliates site will report all SAEs to the OHRS will be responsible for forwarding SAE reports to the IRB and FDA.

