### **13.2 Data Submission Timeline and Forms**

Completion of eCRFs will occur in accordance with NCI guidelines. Baseline (pre-study) eCRFs (e.g., enrollment, medical history, concomitant medications, disease assessment, etc.) will be completed no later than 14 days after the start of treatment. Treatment eCRFs (e.g., drug administration, adverse events, chemistries, etc.) will be completed no later than 14 days following each cycle of treatment. Off-treatment information (e.g., follow-up, best response, etc.) will be completed no later than 14 days after the end of protocol treatment.

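### The adverse-event window closes before the scheduled 30-day postoperative toxicity assessment, so late postoperative events have no clear recording rule and their capture depends on the date of surgery

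*Combined protocol and SAP*

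**What the plan says.** The calendar in Section 6 has a column for 30 days after surgery or XRT. The history and physical examination in that column carries footnote 1: "To include toxicity assessment, ECOG performance status, weight". A window of 2 days either side applies to assessments and 1 day either side to treatment.

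Section 8 sets the period for grading and recording adverse events as those "occurring during the active portion of therapy, or up to 30 days after the last dose of treatment will be graded". Section 8.1 gives serious or unexpected events the same limit: "up to 30 days after the last dose of treatment, will be reported to the OHRS".

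Section 8.1 also contains sentences that state no window of their own:
- the deadlines for notifying the IRB of deaths and other SAEs;
- the duty of affiliate sites to send SAEs to OHRS;
- under the heading on commercially available drugs, a duty to report to the FDA unexpected SAEs associated with cetuximab.

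The order of treatment is in Section 4.1: "The patients will be under active treatment with cetuximab monotherapy for approximately 8 weeks". Then: "Afterwards, they will be assessed for disease response and determination of whether the lesion is potentially resectable will be made". Section 7.2.4 places surgery after the course: "After 8 weeks of neoadjuvant cetuximab, tissue will either be harvested at surgery". No section fixes a date for surgery.

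Section 1.1 makes the safety and feasibility of neoadjuvant cetuximab a co-primary objective.

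**The concern.** The plan schedules a visit to look for toxicity a month after the operation. Its recording rule, however, is anchored to the drug and expires earlier. A complication that begins between the two dates may be seen at the visit without any clear instruction to grade it, enter it on the adverse-event eCRF or report it to OHRS.

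For a drug given before an operation, safety includes harm in the postoperative month, such as impaired wound healing or infection. If the rule is followed as written, whether a complication must be recorded depends on how soon after cetuximab the patient was operated on. Two patients with the same complication at the same postoperative interval could be counted differently. With 20 patients planned, a few events handled inconsistently would change the reported safety rate visibly. Section 1 says the results are meant to lead to a large randomized trial.

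**Working it through.** The plan gives no figure on this point, so there is none to reproduce. The check is calendar arithmetic. The sample-size calculation in Section 15.2 is unaffected.

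**Inputs.** Section 7.2.2 gives eight weekly doses; take dose 1 as day 1. Sections 8 and 8.1 close the window 30 days after the last dose, read here as cetuximab. Section 6 puts the postoperative visit 30 days after surgery. Surgery dates are assumptions. The earliest taken is day 57, the Week 9 evaluation, one week after dose 8.

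**Formulas.** Let L be the day of the last dose and S the day of surgery.
- Dose n falls on day 1 + 7(n − 1), so dose 8 is on day 1 + 49 = 50.
- Window close = L + 30 = 50 + 30 = day 80.
- Visit = S + 30. It falls (S + 30) − (L + 30) = S − L days after the close.
- Postoperative days covered, of 30 = max(0, L + 30 − S).

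**Eight undelayed doses (L = 50, close on day 80).**

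| Surgery | Visit | Days from close to visit | Days covered of 30 |
|---|---|---|---|
| day 57 | day 87 | 7 | 23 (77%) |
| day 64 | day 94 | 14 | 16 |
| day 71 | day 101 | 21 | 9 (30%) |
| day 80 | day 110 | 30 | 0 |

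**Most favourable visit windows.** Dose 8 one day late is day 51, so the close is day 81. Week 9 two days early is day 55. With surgery that day and the visit two days early, the visit is on day 55 + 30 − 2 = 83, still 2 days after the close. On nominal dosing, the visit reaches the window only if surgery is within 2 days of the last dose, which the Week 9 restaging makes implausible.

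**Delays and early stopping.** Delays that move the last dose and Week 9 together leave S − L unchanged. Early stopping widens the gap if surgery still follows Week 9 (assumption, S = 57):
- last dose 7 (day 43): 43 + 30 − 57 = 16 days covered;
- last dose 6 (day 36): 36 + 30 − 57 = 9;
- last dose 4 (day 22): the window closes on day 52, before surgery, so 0.

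**Consequence.** Take a wound infection on postoperative day 20. After surgery on day 57 it starts on day 57 + 20 = 77, inside the window. After surgery on day 71 it starts on day 71 + 20 = 91, outside it.

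**Radiotherapy.** Patients who receive XRT instead share the same calendar column. XRT also follows the Week 9 evaluation, so their visit is no earlier than day 87 on the nominal schedule.

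**The case against.** **There are other reporting rules.** A reader might infer that late postoperative events have no mandatory rule at all. The documents do not support that. The FDA duty in Section 8.1 has no time limit and would catch an unexpected SAE associated with cetuximab after day 80. The IRB and affiliate sentences state no window either. They follow the sentence that does, so their scope is arguable. What clearly lacks a rule is narrower: grading, adverse-event eCRF entry and OHRS reporting under the windowed sentences, above all for events that are non-serious, expected or judged unrelated to cetuximab.

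**The eCRF timetable does not shut off capture.** It is tempting to read Section 13.2 that way. It says "Treatment eCRFs (e.g., drug administration, adverse events, chemistries, etc.) will be completed no later than 14 days following each cycle of treatment" and "Off-treatment information (e.g., follow-up, best response, etc.) will be completed no later than 14 days after the end of protocol treatment", and the second deadline would be day 50 + 14 = 64 if protocol treatment ends with cetuximab. But the lists are illustrative, follow-up is named among the off-treatment items, and two years of visits supply progression and survival. A 14-day deadline cannot end data capture. Section 13.1 also refers to a data capture plan that is not among these documents, and Section 13.3 keeps source documents for Grade 3–4 events without a 30-day limit. So Section 13 does not create the gap, but neither does it state a rule that fills it.

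**The last dose is not defined.** Section 17 lists surgery and radiation as treatment modalities, and radiation does have a dose. That stands as an ambiguity. Still, Section 17 concerns payment, an operation has no dose, and Sections 4.1 and 7.1 point to cetuximab as the active and experimental treatment. If the sponsor meant the window to run from local therapy, the text needs to say so.

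**The reach is limited.** Surgery is only a possibility for each patient, most of the postoperative month is covered if it happens at Week 9, and the safety objective has no numerical threshold that these events would cross. All of that is true. It limits the size of the problem but does not remove the mismatch between the window and the visit.

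**Conclusion.** The concern holds in this form: with the last dose read as cetuximab, the stated window closes before the 30-day postoperative toxicity assessment for any realistic surgery date. Events that start in between have no clear rule for grading, adverse-event eCRF entry or OHRS reporting. On an undelayed course, the uncovered part of the postoperative month is 7 of 30 days for surgery on day 57, 21 for day 71 and all 30 from day 80. Capture of postoperative harm, part of a co-primary objective, then depends on the surgery date.

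This rests on two assumptions: the cetuximab reading of the last dose, and surgery no earlier than Week 9. A reader might go on to infer that a material number of complications will be lost. The documents give no surgery dates, number operated or complication rate, so no such number can be estimated. On-treatment capture, events that begin inside the window, and deaths (overall survival is an endpoint) are not in question.

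**What to change.** In Sections 8 and 8.1, state that the last dose means cetuximab. Collect adverse events and SAEs until the later of 30 days after that dose and the scheduled 30-day visit after surgery, or after XRT for patients who receive it instead. State in Section 13.2 that toxicity found at that visit is entered on the adverse-event eCRF. Report these events on a separate line, with attribution (cetuximab, local therapy or both) and with the patients who had surgery (or XRT) as the denominator.

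The cost is wording and some extra event forms. The visit, examination, blood count, chemistries, liver enzymes and toxicity assessment are already scheduled. The drawback is that some recorded events will be due to local therapy rather than cetuximab, and a single-arm trial cannot separate the two by comparison. Attribution will rest on the investigator's judgment, and the report should say so.

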## 7. Treatment Plan

**7.1 General Considerations** The experimental aspect of this protocol is in the use of neoadjuvant cetuximab monotherapy in these patients with locally advanced or recurrent SCCS. Once treatment response to cetuximab monotherapy is established, the determination of patient tolerance to the selected dose and disease response/potential resectability of the lesion will be determined.

### 7.2 Sequence of treatment

#### 7.2.1 Prior to neoadjuvant cetuximab

Patients will be staged using imaging to delineate the extent of disease. Initial biopsy specimen (preferably a core biopsy as opposed to a FNA) will be procured from the primary cutaneous site. If the patient is found to have regional lymph node involvement, core biopsy of accessible node will also be obtained. Samples will be used for confirmation of diagnosis as well as DNA and RNA genotyping. These specimens will be flash frozen and brought that same day to the Biospecimen Repository Service (BRS).

#### 7.2.2 Neoadjuvant Cetuximab

Patients who agree and are eligible for this protocol will initially receive 8 weeks of neoadjuvant cetuximab. The initial dose of cetuximab will be  $400 \text{ mg/m}^2 \text{ IV}$ , followed by

weekly doses of cetuximab  $250 \text{ mg/m}^2$  IV to complete 8 total weeks of treatment. Even if a patient is found to have a cetuximab related folliculitis, they will complete the scheduled 8 weeks of neoadjuvant cetuximab.

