#### **7.3.3 Dose Modifications or Escalations**

##### **7.3.3.1 Cetuximab related Folliculitis**

Patients will concomitantly be assessed for the presence of cetuximab related folliculitis given the published correlation of folliculitis with clinical benefit (Bonner 2006). After MD visits, the patient will be assessed for the development of folliculitis characteristic of EGFR inhibition. Though the rash associated with EGFR inhibition appears similar to acne vulgaris and is commonly referred to as acne, acne-like, or acneiform, these terms are technically inaccurate. EGFR-associated rash is dominated by pustules that contain an intrafollicular collection of neutrophils—the hallmarks of an infectious folliculitis. Per Perez-Soler, the typical EGFR associated rash has a clinical presentation

characterized by pustular/popular appearance, usually involving the face, head, and upper torso, and often accompanied by pruritus, dry skin, and erythema (Perez-Soler, Zou et al. 2011).

In previous reports, the criteria used for significant EGFR associated rash has most commonly been grade 2+ on the CTCAE 4.0 criteria listed below.

CTCAE 4.0 Criteria

	1	2	3	4
Pruritus/itching	Mild or localized	Intense or widespread	Intense or widespread and interfering with ADL	—
Rash/Desquamation	Macular or papular eruption or erythema without associated symptoms	Macular or papular eruption or erythema with pruritus or other associated symptoms; localized desquamation or other lesions covering < 50% of body surface area (BSA)	Severe, generalized erythroderma or macular, papular or vesicular eruption; desquamation covering > 50% BSA	Generalized, exfoliative, ulcerative, or bullous dermatitis
Rash/Acneiform	Intervention not indicated	Intervention not indicated	Associated with pain, disfigurement, ulceration, or desquamation	—
Nail Changes	Discoloration; Ridging (koilonychias); pitting	Partial or complete loss of nail(s); pain in nail bed(s)	Interfering with ADL	—

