Acneform rash usually developed within the first two weeks of therapy and resolved in a majority of the patients after cessation of treatment, although in nearly half, the event continued beyond 28 days. Monitor patients receiving Cetuximab for dermatologic toxicities and infectious sequelae. Instruct patients to limit sun exposure during Cetuximab therapy.

Rash occurring with Cetuximab administration may be graded according to the following table from CTCAE 4.0.

	1	2	3	4
Pruritus/itching	Mild or localized; topical intervention indicated	Intense or widespread; intermittent; skin changes from scratching (e.g., edema, papulation, excoriations, lichenification, oozing/crusts); oral intervention indicated; limiting instrumental ADL	Intense or widespread; constant; limiting self care ADL or sleep; oral corticosteroid or immunosuppressive therapy indicated	–
Purpura	Combined area of lesions covering <10% BSA	Combined area of lesions covering 10 - 30% BSA; bleeding with trauma	Combined area of lesions covering >30% spontaneous bleeding BSA;	–
Rash/acneiform	Papules and/or pustules covering <10% BSA, which may or may not be associated with symptoms of pruritus or tenderness	Papules and/or pustules covering 10 - 30% BSA, which may or may not be associated with symptoms of pruritus or tenderness; associated with psychosocial impact; limiting	Papules and/or pustules covering >30% BSA, which may or may not be associated with symptoms of pruritus or tenderness; limiting self care ADL; associated with local superinfection with oral antibiotics	Papules and/or pustules covering any % BSA, which may or may not be associated with symptoms of pruritus or tenderness and are associated

		instrumental ADL	indicated	with extensive superinfection with IV antibiotics indicated; life- threatening consequences
Rash/maculo-papular	Macules/papules covering <10% BSA with or without symptoms (e.g., pruritus, burning, tightness)	Macules/papules covering 10 - 30% BSA with or without symptoms (e.g., pruritus, burning, tightness); limiting instrumental ADL	Macules/papules covering >30% BSA with or without associated symptoms; limiting self care ADL	
Nail Discoloration	Asymptomatic; clinical or diagnostic observations only; intervention not indicated	—	—	—
Nail Loss	Asymptomatic separation of the nail bed from the nail plate or nail loss	Symptomatic separation of the nail bed from the nail plate or nail loss; limiting instrumental ADL	—	—

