Nail Ridging	Asymptomatic; clinical or diagnostic observations only; intervention not indicated	—	—	—

Cetuximab dose should be modified per the following table in case of severe (grade 3/4) rash:

Occurrence of Severe (Grade3/4) acneiform	Cetuximab modification
---	------------------------

rash	
1 st Occurrence	Delay infusion 1 to 2 weeks. If there is improvement, continue cetuximab at at 250 mg/m  . If there is no improvement, discontinue cetuximab.
2 nd Occurrence	Delay infusion 1 to 2 weeks. If there is improvement, continue cetuximab at at 200 mg/m  . If there is no improvement, discontinue cetuximab.
3 rd Occurrence	Delay infusion 1 to 2 weeks. If there is improvement, continue cetuximab at at 150 mg/m  . If there is no improvement, discontinue cetuximab.
4 th Occurrence	Discontinue cetuximab

For the occurrence of grade 1 or 2 rash, see supportive care guidelines in section 7.4.5.1.

**7.3.4 Dose modifications for other toxicity:** due to lack of evidence that cetuximab contributes to these toxicities, cetuximab dose will not be altered for renal failure, fatigue, nausea/vomiting.

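### Section 7.2.2 has every patient with cetuximab folliculitis complete 8 weeks, while the 7.3.3.3 table stops some with grade 3/4 rash; and two differing tables, both labelled CTCAE 4.0, define acneiform grade 3

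*Combined protocol and SAP*

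**What the plan says.** **Regimen.** Section 7.2.2, after giving the dose and schedule, says: "Even if a patient is found to have a cetuximab related folliculitis, they will complete the scheduled 8 weeks of neoadjuvant cetuximab". It has no grade qualifier and no reference to the dose-modification rules.

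**Terminology.** Section 7.3.3.1 uses folliculitis as the protocol's name for the rash of EGFR inhibition, which it says is "commonly referred to as acne, acne-like, or acneiform, these terms are technically inaccurate". Folliculitis and acneiform rash are therefore the same event here.

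**Dose rule.** Section 7.3.3.3 says: "Cetuximab dose should be modified per the following table in case of severe (grade 3/4) rash". At each of the first three occurrences of grade 3/4 acneiform rash the infusion is delayed 1 to 2 weeks, and then: "If there is no improvement, discontinue cetuximab". At the 4th occurrence cetuximab is stopped outright.

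**Grading.** Section 9.1 makes weekly folliculitis grading mandatory and sends it to the criteria in 7.3.3.1. That table, labelled CTCAE 4.0, gives acneiform grade 3 as "Associated with pain, disfigurement, ulceration, or desquamation" and leaves grade 4 blank. Section 7.3.3.3 has its own table, introduced in permissive terms: "Rash occurring with Cetuximab administration may be graded according to the following table from CTCAE 4.0". There, acneiform grade 3 begins "Papules and/or pustules covering >30% BSA, which may or may not be associated with symptoms of pruritus or tenderness; limiting self care ADL" and adds local superinfection needing oral antibiotics; a grade 4 is also defined.

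**The concern.** Two instructions about the same event disagree. A patient with severe rash that does not settle must finish treatment under one section and stop under another. Deciding that the dose table wins does not remove the second problem: the table is triggered by grade 3/4, and the protocol defines that grade in two ways.

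At stake are the dosing of patients with severe rash and the count of grade 3/4 rash. Safety and feasibility form a co-primary objective in Section 1.1, and rash is the toxicity for which the protocol gives its most detailed dose-reduction schedule.

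**Working it through.** **1. The plan's own figures.** Section 15.2 gives N = 20, a null rate of 10%, an expected rate of 30% and a one-sided exact binomial test. Rejecting at 5 or more responses:
- P(X ≥ 5 | 20, 0.10) = 4.32%, as stated.
- P(X ≥ 5 | 20, 0.30) = 76.25%, against 76.2% stated.

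Both reproduce. Neither depends on how rash is graded or managed.

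**2. Section 7.2.2 against the 7.3.3.3 dose table.**

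| Situation | 7.2.2 | 7.3.3.3 | Consistent? |
|---|---|---|---|
| Grade 1/2 | complete 8 weeks | supportive care | yes |
| Grade 3/4, improves after delay, 1st to 3rd occurrence | complete the scheduled 8 weeks | delay, then resume (reduced dose from the 2nd) | conflict over timing only |
| Grade 3/4, no improvement after delay | complete 8 weeks | discontinue | no |
| Grade 3/4, 4th occurrence | complete 8 weeks | discontinue | no |

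The flat contradiction is confined to the last two rows.

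**3. The two grading tables.** I compare the acneiform rows, because the dose table is headed for acneiform rash.
- *Painful pustules on 8% BSA.* On 7.3.3.1, pain meets grade 3, so the infusion is held. On 7.3.3.3, grade 1 is "Papules and/or pustules covering <10% BSA, which may or may not be associated with symptoms of pruritus or tenderness", so there is no hold.
- *Painless pustules on 35% BSA that limit self care and need oral antibiotics for local superinfection, with no disfigurement, ulceration or desquamation.* On 7.3.3.3 this is grade 3, so the infusion is held. On 7.3.3.1 none of the grade 3 features is present, so there is no hold.

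The discrepancy runs in both directions: grading as 9.1 directs can trigger a hold that the 7.3.3.3 table would not, and can miss one that it would require. Grades 1 and 2 of the 7.3.3.1 acneiform row also read identically in the available text. That may be a copying slip, and nothing here depends on it.

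**4. Scale.** Inputs are N = 20 (Section 4.1) and severe acneiform rash in 1–17% of patients in cetuximab trials (7.3.3.3).
- 20 × 0.01 = 0.2 patients
- 20 × 0.17 = 3.4 patients

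These are expected numbers with severe rash. The protocol gives no rate of non-improvement or of a 4th occurrence, so the number discontinued cannot be computed.

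**The case against.** The best answer is that the intent is clear from the whole protocol. Section 12.2 says to withhold for severe, persistent rash and to reduce the dose for recurrent severe rash. Section 10 allows for treatment delays due to adverse events and lets the investigator stop treatment when a patient's condition makes it unacceptable. Section 16.2 says rash will be monitored as set out in 7.3.3. Against these stands one general sentence in 7.2.2. This is persuasive about intent, and I accept that most readers would follow the dose table. But none of these places says which section prevails, and 7.2.2 is where the regimen is prescribed.

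On grading, Sections 8 and 9 tie adverse events and weekly rash assessment to CTCAE 4.0, a published standard that a site could consult. The 7.3.3.3 table also stands just above the dose rule and is probably the intended source. That limits the practical ambiguity but does not close it. Both tables carry the CTCAE 4.0 label, the mandatory wording in 9.1 points to 7.3.3.1, and the wording in 7.3.3.3 is only permissive.

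A reader might also infer that delayed or stopped patients have conflicting CT dates between Section 6 (Week 9) and 7.2.3.1 (after 8 weeks of cetuximab). The documents do not support that as a definite conflict. A gap arises only if Week 9 is fixed from the first dose and held doses are made up, and the protocol states neither. The column is headed as a post-cetuximab visit, and Week 9 can be read as its nominal time for an undelayed course.

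**Conclusion.** Wrong as written, on two counts. First, 7.2.2 contradicts the 7.3.3.3 dose table for grade 3/4 rash that fails to improve or occurs a 4th time. Second, the grade that triggers a hold has two definitions, and the one that 9.1 makes mandatory is not the one placed with the dose rule.

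The 0.2 to 3.4 patients with severe rash assume that the 1–17% rate carries over to this population and to 8 weeks of treatment. The conflict over discontinuation affects only a subset of them, of unstated size. A reader might take the chance of at least one severe case, 1 − 0.99^20 = 18% to 1 − 0.83^20 = 98%, as the chance that the contradiction arises. It is not: it counts any severe rash, including rash that improves and is handled without a flat contradiction.

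Nor does the point show that the safety endpoint is undefined, that sites would in practice treat through unresolved severe rash, or that the response test is compromised. It is a narrow inconsistency in a safety instruction, worth correcting because it is cheap to remove.

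**What to change.** - **7.2.2:** limit the sentence to grade 1–2 folliculitis and add that grade 3/4 is managed under 7.3.3.3.
- **9.1:** replace the reference to the 7.3.3.1 table with the grading table in 7.3.3.3, and use that one table throughout for grading and for dose holds.

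One clerical item can be corrected at the same time: for grade 1/2 rash, 7.3.3.3 refers to section 7.4.5.1, whereas the rash guidance is at 7.3.6.1.

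The cost is a short amendment. No visit, scan, dose level or sample size changes.
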